Early Gestational Diabetes Screening in Gravid Obese Women

(EGGO)

Protocol

(Version 1.1; 02.17.2014)

Study Procedures

1. **Screening.** Records of health clinic patients will be reviewed by trained research staff to identify eligible patients. Eligible patients will receive a letter and/or phone call notifying them of their eligibility and asking them to participate. Trained research staff will be available at the OB Complications clinic and ultrasound to **screen** and **consent** patients. A screening log or form will be used to track all patients approached for the study. Women will be randomized at the time of consent. At the time of consent, women will sign a maternal/infant medical record release which will be faxed to any hospitals to obtain records for review if necessary.
2. **Randomization.** A confidential, computer-generated simple randomization scheme will be prepared by a designated study biostatistician. Randomization will be stratified by morbid obesity (BMI>40.0). Women will be randomized after they give consent by pulling the next sequential envelope from the participant's BMI group that will disclose whether the participant is assigned to early or routine timing of the GDM screen.
3. **Gestational Diabetes Screening.**
 - a. **Early Screening Group.**
 - i. Women assigned to "early screening" will complete the BSST (50-g glucose load) between 14 weeks, 0 days gestation and 20 weeks, 0 days gestation. If the test cannot be completed due to nausea or vomiting, the patient may choose to re-schedule another attempt prior to 20 weeks, 0 days or she may choose to withdraw from the study.
 1. If a participant is between 14 weeks, 0 days and 20 weeks, 0 days at the time of randomization she may:
 1. Choose to undergo BSST at the time of randomization in OBCC clinic. Add EGGO to her problem list with a message that she was randomized to early screening & the date of completion of the BSST.
 2. Choose to undergo BSST at next appointment at her local clinic. If she chooses this option, place a message in IMPACT and EGGO to her problem list with her randomization group. This will notify her provider to complete the BSST at the next visit prior to 18 weeks.
 - ii. At the time of the BSST, a purple and gold top tube will be drawn for HbA1c & Glycomark (refer to baseline procedures below). These specimens will be labeled with the patient name plate and sent to the OBGYN lab for testing.

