 - iii. In those who are not diagnosed with GDM at the early screen, repeat testing will be performed at 24-28 weeks.
 - b. **Routine Screening Group.**
 - i. Women assigned to routine screening will have a blood draw for HbA1c and Glycomark between 14 weeks, 0 days and 20 weeks, 0 days gestation.

- If HbA1c $\geq 6.3\%$ in the routine screening group, the result will be unblinded and the clinician informed. These women will subsequently enter into routine GDM care with dietary counseling and patterned blood sugars.
 - If the patient is between 14 weeks, 0 days and 20 weeks, 0 days this blood draw may be performed at the enrollment visit. Otherwise, may be done in clinic with routine prenatal labs.
- ii. Women assigned to “routine screening” will undergo the 1-hour, 50-g glucose load (BSST) between 24 weeks, 0 days and 28 weeks, 0 days gestation. At the time of the BSST, a purple & gold top tube for HbA1c & Glycomark will be drawn (see baseline procedures below).

4. Results of Glucose screening tests

- a. Women whose BSST is ≥ 135 mg/dL, will be scheduled to undergo diagnostic testing with a 3-hour GTT (100-g glucose load). The currently used criteria to diagnose GDM (Carpenter Coustan criteria) will be used to diagnose GDM. By these criteria, a woman must have 2 elevated blood sugar values at either of the following timepoints and values:
1. Fasting ≥ 95 mg/dL
 2. 1-hour ≥ 180 mg/dL
 3. 2-hour ≥ 155 mg/dL
 4. 3-hour ≥ 140 mg/dL
- b. The attending physician will review the three-hour GTT results to confirm the diagnosis of GDM.
- c. Women who have a BSST > 200 will have a fasting blood sugar checked prior to undergoing a 3-hour GTT. If the fasting blood sugar < 126 mg/dL, the patient will proceed with a 3-hour GTT. If the fasting blood sugar ≥ 126 mg/dL, the diagnosis of GDM will be made.
- d. Women who are not diagnosed with GDM between 14-20 weeks (i.e. women who have a normal 1-hour BSST or who have an elevated 1-hour BSST but a normal 3-hour GTT) will repeat the 1-hour BSST at 24-28 weeks. At the time of the repeat BSST, a purple & red top tube for HbA1c & Glycomark will be drawn (see baseline procedures below).
- i. Women who are diagnosed with GDM will enter into routine GDM care with dietary counseling and patterned blood sugars. A purple & gold top tube for HbA1c & Glycomark will be drawn between 24-28 weeks, and 0 days gestation (see baseline procedures below).

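### The deferred early glucose screen has an 18-week deadline that women randomized at 18w0d to 19w6d cannot meet, and nothing ties the deferred visit to the 20-week limit

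*Protocol*

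**What the plan says.** Gestational ages are written here as weeks and days, so 18w0d is 18 weeks 0 days.

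**Protocol, Study Procedures item 3.a.i (Early Screening Group).** The governing rule is that Early women have the BSST "between 14 weeks, 0 days gestation and 20 weeks, 0 days gestation". If nausea or vomiting prevents completion, the woman may "re-schedule another attempt prior to 20 weeks, 0 days" or withdraw. A woman who is "between 14 weeks, 0 days and 20 weeks, 0 days at the time of randomization" has two options:

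- "Choose to undergo BSST at the time of randomization in OBCC clinic"; or
- "Choose to undergo BSST at next appointment at her local clinic". For this option staff are to "place a message in IMPACT and EGGO to her problem list with her randomization group", which is meant to prompt the provider to "complete the BSST at the next visit prior to 18 weeks".

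**Protocol item 8.a.iii (Randomization Form).** Gestational age must be below 20w0d. No lower limit is given.

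**Protocol item 3.b.ii (Routine Screening Group).** Routine women "will undergo the 1-hour, 50-g glucose load (BSST) between 24 weeks, 0 days and 28 weeks, 0 days gestation".

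**SAP.** Section 1 gives 14-20 weeks for early and 24-28 weeks for routine screening, in line with the protocol. Section 2 labels the groups 14-18 and 20-24 weeks. The Specific Aim 2 statement (section 4.1) says 14-18 weeks, while its hypothesis (section 4.1.1) covers everyone randomized to Early.

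**The concern.** The trial tests the timing of screening, so the instruction that gets the early test done on time is the instruction that delivers the intervention. The deferral option hands that task to a local provider. The deadline passed on is two weeks shorter than the governing window, and some of the women offered the option have already passed it.

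The option also lacks the safeguard that matters more: it does not ask when the next visit is. A woman randomized late in the window could defer to a visit after 20w0d and so have no valid early screen. Under intention-to-treat she stays in the Early group, and each such case would bring the two arms closer together. The plan can close this gap in advance at almost no cost.

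The SAP labels are a lesser matter. They misdescribe the timing of the arms and could be carried into table titles or reports.

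**Working it through.** The documents give no figure to reproduce on this point. The check compares the stated windows and counts gestational days.

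**Inputs**

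- Early window: 14w0d to 20w0d (protocol 3.a.i; also item 4.d and SAP section 1).
- Ages at which deferral is offered: 14w0d to 20w0d (protocol 3.a.i).
- Upper limit for randomization: below 20w0d, so the last day is 19w6d (protocol 8.a.iii).
- Deadline for the deferred test: before 18w0d (protocol 3.a.i).
- Routine window: 24w0d to 28w0d (protocol 3.b.ii; also SAP section 1).
- Interval to the next clinic visit: not given. It is assumed below to be 1 to 4 weeks.

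**Step 1: when the clause is impossible.** Randomization days covered by the option, 14w0d to 19w6d: 6 × 7 = 42. Days at or after 18w0d, 18w0d to 19w6d: 2 × 7 = 14. Share of days: 14/42 = 33%. On each of these 14 days the deadline has already been reached. Reading the 18-week phrase as describing the visit rather than the test does not help, because no future visit can fall before 18 weeks. On that reading the clause simply gives these women's providers no instruction.

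**Step 2: when the next visit misses 18 weeks or 20 weeks.** Let the next visit be k weeks after randomization. It falls at or after 18w0d on 14 + 7k of the 42 days, and after 20w0d on 7k − 1 of them. The difference, always 15 days, is the set of visits from 18w0d to 20w0d: inside the governing window but outside the clause.

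| Assumed k (weeks) | First randomization age whose next visit misses the 18-week clause | Days missing the clause | Of these, visit by 20w0d | Of these, visit after 20w0d |
|---|---|---|---|---|
| 1 | 17w0d | 21 | 15 | 6 |
| 2 | 16w0d | 28 | 15 | 13 |
| 3 | 15w0d | 35 | 15 | 20 |
| 4 | 14w0d | 42 | 15 | 27 |

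The 14 days in step 1 are therefore a minimum that needs no assumption about visits. The last column shows why moving the deadline to 20w0d is not enough: some deferred visits would fall after 20w0d, and the option has no check for this.

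**Step 3: SAP labels.** The routine window 24w0d to 28w0d has 4 × 7 + 1 = 29 days. The section 2 label of 20-24 weeks shares 1 of these if 24 weeks means 24w0d, or 7 if it means the completed week 24w0d to 24w6d. Either way it is not a narrower target inside the real window. The 14-18 week labels in section 2 and Specific Aim 2 do lie inside 14-20 weeks, but leave out its later part.

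**Step 4: what depends on these windows.** SAP 3.1.2 analyses every randomized woman in her assigned group, whether or not the screening plan was followed. SAP 3.1.3 builds the sample size from a 50% event rate, a 50% reduction and a 10% incidence of gestational diabetes. The stopping values in 3.2 come from an alpha spending function. None of these uses a screening window.

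**The case against.** The strongest reply is that the operative rule is the 14w0d to 20w0d window, and that the 18-week phrase only describes what a chart message should prompt. It excludes nobody and attaches no consequence to passing 18 weeks. An earlier target could leave time for a repeat attempt or a 3-hour test before 20 weeks, although the protocol states no such purpose. A woman at 18w0d or later can be tested the same day, or at a next visit by 20w0d. On the SAP side, section 2 selects no data and the Aim 2 hypothesis already names the whole Early group.

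Much of this stands, and it limits the consequence. But the protocol does not call 18 weeks a target, and it could not be one for women already past it. The reply also leaves the missing check on the date of the next visit unanswered.

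Three stronger readings are tempting, and the documents support none of them:

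- *That women past 18 weeks will go untested.* Nothing tells a provider to skip a late test. The message wording is not in the documents; the protocol says only that it carries the randomization group.
- *That a third of Early women are affected.* The third is a share of days. The documents give neither the distribution of gestational age at randomization nor the proportion who defer, and women may also be randomized before 14w0d.
- *That the SAP labels move the Routine test or shrink the Aim 2 analysis.* The Routine instruction in protocol 3.b.ii is clear, and sections 4.1.1 and 4.1.2 set no 18-week cut-off.

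**Conclusion.** The point holds as a defect in one operative clause. Protocol 3.a.i offers deferral to women for whom its own deadline is impossible, contradicts the 20-week limit in the same item, and does not check that the deferred visit falls inside the window. The impossible range is 18w0d to 19w6d, which is 14 of 42 randomization days. This takes the Randomization Form's limit of below 20w0d as the upper bound for randomization. The ranges for assumed visit intervals illustrate the gap and do not estimate its frequency. No count of affected women or missed tests follows from the documents.

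The SAP windows in section 2 and Specific Aim 2 are label errors. The primary intention-to-treat method, the sample size and alpha do not change. The correction is worth making because the clause governs delivery of the randomized early screen.

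**What to change.** **Protocol 3.a.i, local-clinic option.** Change the deadline so that the deferred BSST is done at the next visit and no later than 20 weeks, 0 days. Offer deferral only if that visit is booked for 20w0d or earlier. Otherwise test the same day at randomization, which the item already allows. If 18 weeks is wanted as a preferred time, call it a target.

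**SAP section 2.** Label the groups Early 14-20 weeks and Routine 24-28 weeks.

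**SAP section 4.1.** Change 14-18 to 14-20 weeks, and leave the population in 4.1.1 as it is.

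**Cost.** One reworded protocol clause with an added condition, and a few words in two SAP sections. Staff must check the date of the next appointment before offering deferral. Women whose next visit falls after 20w0d have slightly less choice. No new data are needed, and no analysis changes.

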- ii. Women who are not diagnosed with GDM (i.e. women who have a normal 1-hour BSST or who have an elevated 1-hour BSST but a normal 3-hour GTT) will continue routine prenatal care.
- iii. Women who are diagnosed with GDM will enter into routine GDM care with dietary counseling and patterned blood sugars.

5. Baseline Procedures

- Measurement of height, without shoes, at time of enrollment.
- Record self-reported prepregnancy weight.
- All women will have a blood draw for HbA1c and Glycomark between 14 weeks, 0 days and 20 weeks, 0 days gestation. The blood for HbA1c should be collected in a purple top tube (3mL). The blood for Glycomark should be collected in a gold top tube (3mL).
 - Women undergoing early GDM screening may have these blood samples drawn at the time of the blood draw for the 1-hour BSST.
 - Women randomized to routine screening may have these blood samples drawn at the time of randomization if between 14 weeks, 0 days and 20 week, 0 days. Otherwise, they may have the blood drawn at their clinic at an appropriate time (i.e. at the time of other routine prenatal lab draws).
 - Samples will be labeled with patient name plate for transport to OBGYN lab.
 - Samples may be stored at room temperature or 4°C (refrigerated) for up to 7 days.
- All women will have a blood draw for HbA1c and Glycomark between 24 weeks, 0 days and 28 weeks, 0 days gestation. The blood for HbA1c should be collected in a purple top tube (3mL). The blood for Glycomark should be collected in a gold top tube (3mL).
 - This blood draw may be performed at the time of the 1-hour BSST.
 - Women diagnosed with GDM prior to 24-28 weeks may have the blood drawn in clinic at the appropriate gestational age, in conjunction with routine prenatal lab draws or separately.
 - Samples will be labeled with patient name plate for transport to OBGYN lab.
 - Samples may be stored at room temperature or 4°C (refrigerated) for up to 7 days.
- Trained and experienced research staff in obstetric and perinatal outcomes abstraction will be responsible for all research data abstraction from patient medical records.
- Maternal outcomes will be ascertained in the hospital following delivery and at the routinely scheduled follow-up visit at 4-6 weeks after delivery.
- Newborn outcomes will be ascertained until 6 weeks after delivery through maternal questioning regarding re-admission. Readmissions for infants will be validated through medical review.

6. Follow-up

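### An HbA1c of 6.3% or more at 14-20 weeks triggers GDM care in the Routine arm only; for the Early arm the plan states no masking, disclosure or action for the same result.

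*Protocol*

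**What the plan says.** HbA1c is measured early in both arms. Protocol 5 (Baseline Procedures): "All women will have a blood draw for HbA1c and Glycomark between 14 weeks, 0 days and 20 weeks, 0 days gestation". Protocol 3.a.ii places the Early-arm sample at the early screen: "At the time of the BSST, a purple and gold top tube will be drawn for HbA1c & Glycomark". Protocol 3.b.i places the Routine-arm sample in the same gestational window.

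A rule for acting on the result appears once, in Protocol 3.b.i. At 6.3% or more "in the routine screening group, the result will be unblinded and the clinician informed". The consequence is care, with no BSST or GTT required first: "These women will subsequently enter into routine GDM care with dietary counseling and patterned blood sugars".

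For the Early arm, Protocol 3.a gives no HbA1c threshold, disclosure or action. Entry to care depends on BSST, GTT or fasting glucose (Protocol 4.a to 4.c). Protocol 3.a.iii adds: "In those who are not diagnosed with GDM at the early screen, repeat testing will be performed at 24-28 weeks". Protocol 4.d defines the undiagnosed by BSST and GTT alone: "women who have a normal 1-hour BSST or who have an elevated 1-hour BSST but a normal 3-hour GTT) will repeat the 1-hour BSST". That repeat test falls in the 24-28 week window, and HbA1c has no part in the definition. The SAP does not mention the 6.3% rule.

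**The concern.** The trial compares identifying GDM at 14-20 weeks with identifying it at 24-28 weeks. For women at or above the threshold, the written rule can remove that contrast, because Routine is treated early. It can also reverse it, because Routine is treated early while Early waits.

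The safety side needs no assumed rate. The protocol treats a value of 6.3% or more as serious enough to break masking and begin care in one arm, and is silent about the same value in the other. The word unblinded implies that HbA1c is otherwise masked in Routine; its status in Early is not stated, so care there could vary by clinician.

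The statistical side is dilution. The primary analysis is intention-to-treat (SAP 3.1.2), so these women stay in their assigned arm. If earlier care helps, as the trial hypothesises, both effects pull the difference toward zero.

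**Working it through.** **1. The two pathways side by side.** Take a constructed case: HbA1c at or above 6.3% and BSST 130 mg/dL at 16 weeks.

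| | Routine | Early |
|---|---|---|
| HbA1c drawn at 14-20 weeks | yes (3.b.i, 5) | yes (3.a.ii, 5) |
| Stated action on 6.3% or more | disclosed, GDM care begins | none stated |
| BSST 130 (below 135) | not tested this early | counts as normal (4.a, 4.d) |
| Next protocol trigger for care | already in care | repeat BSST at 24-28 weeks |

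From the early sample to the next Early-arm test: shortest 24w0d - 20w0d = 4 weeks; longest 28w0d - 14w0d = 14 weeks.

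**2. The SAP's own figure.** SAP 3.1.3 assumes 50% against 25% among GDM women, with 80% power; SAP 3.1.2 sets a two-sided 0.05 level. With pooled variance and no continuity correction, mean rate 0.375:

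n = [1.96 × √(2 × 0.375 × 0.625) + 0.8416 × √(0.50 × 0.50 + 0.25 × 0.75)]² / 0.25² = 57.7, so 58 per group (power 80.2%).

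Then 58 / 0.10 = 580 per group and 2 × 580 = 1,160. The figures reproduce. Over all randomized women the implied difference is 0.10 × 25 = 2.5 points, if women without GDM have equal rates in both arms.

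**3. Dilution.** Let f be the share of GDM women at or above 6.3%, equal across arms in expectation because of randomization. Let m be the share of those women whom the early BSST/GTT misses in Early. Neither is in the documents. Assume that early care through HbA1c gives the full early-care benefit and that missed Early women get none.

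- Routine rate = 0.50 - 0.25f
- Early rate = 0.25 + 0.25fm
- Difference in GDM women = 0.25 × (1 - f - fm)
- Difference over all randomized = 2.5 × (1 - f - fm) points

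| f | m = 0 | m = 0.5 | m = 1 |
|---|---|---|---|
| 5% | 2.375 | 2.3125 | 2.25 |
| 10% | 2.25 | 2.125 | 2.0 |

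In the SAP's GDM-only calculation (58 per group, alpha 0.05), power falls from 80.2% to 76.2%, 73.7% and 71.2% across the first row, and to 71.8%, 66.4% and 60.7% across the second.

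**4. Against the test actually planned.** The primary test uses all randomized women, 580 per group. The documents give no overall composite rate; for an assumed 30% to 50%, the standard error of the difference is √(2 × 0.30 × 0.70 / 580) = 2.7 points to √(2 × 0.50 × 0.50 / 580) = 2.9 points. The largest loss in the table is 2.5 - 2.0 = 0.5 points, and 0.5 / 2.7 is just under 0.2 standard errors.

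**5. What a common rule would recover.** Acting on the result in both arms removes only the fm term and leaves 2.5 × (1 - f). At f = 10% and m = 1 the difference moves from 2.0 to 2.25, not back to 2.5. Acting in neither arm removes only the f term and leaves 2.5 × (1 - fm).

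**The case against.** The best defence is that this is a safety net with an evident purpose. Routine women have no protocol glucose test before 24 weeks, whereas Early women have a BSST at 14-20 weeks and a GTT if it is raised. Protocol 3.b.i governs one arm and 3.a the other, so no two passages strictly contradict each other. This stands as an explanation, but it does not cover the Early woman with a high HbA1c and a negative BSST or GTT.

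Three stronger readings are tempting, and the documents do not support them.

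- *A reader might infer that Early women are denied care on a high HbA1c.* The plan is silent on masking in Early, and nothing in 3.a or 4.d bars a clinician who sees the value from acting. What the text supports is that no protocol trigger exists.
- *A reader might infer a substantial loss in the primary comparison.* The largest losses above need m = 1, meaning that the early BSST/GTT misses every woman above the threshold. Many of them may well be found by the early screen; the documents give no overlap figure.
- *A reader might infer that a common rule would restore the full contrast.* It would not. Part of the dilution comes from having any early backstop in Routine.

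There is also a real cost. If HbA1c led to care in Early women negative on BSST/GTT, it would add a second route to treatment in that arm and would treat some of the women used in SAP 4.1 to relate early glucose to outcomes.

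**Conclusion.** The point holds as an arm-specific rule with no counterpart. Followed as written, the same early HbA1c result starts GDM care in Routine and has no protocol trigger in Early for 4 to 14 weeks. That much rests on the text alone.

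It is mainly a patient-safety inconsistency. The dilution is probably small: with f of 5% to 10%, the 2.5-point difference falls to somewhere between 2.375 and 2.0 points, depending on m. This rests on assumed f and m, on full benefit from HbA1c-triggered care, and on equal rates in women without GDM. The documents cannot narrow the range. The drops in GDM-only power show sensitivity in the SAP's sample-size argument; they are not the power of the planned intention-to-treat test.

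The change should be made because the result is already collected in both arms and a consistent rule costs little, not because the primary analysis is shown to be compromised.

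**What to change.** - Reconcile Protocol 3.a, 3.b.i and 4.d so that the 14-20 week HbA1c is masked, disclosed and handled in the same way in both arms. The threshold and the action are for the investigators to set. If a difference between arms is intended, state it and justify it.
- State whether a Routine woman who enters care through HbA1c alone counts as having GDM, and whether her 24-28 week BSST remains diagnostic. SAP 4.2.2 depends on GDM status at that time.
- In the SAP, report by arm, next to the primary result, the number at or above the threshold and the number entering GDM care through HbA1c rather than BSST/GTT.

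**Cost.** A short protocol amendment and one SAP table. The sample is already drawn and sent for testing in both arms, and the Diabetes Testing Form (Protocol 8.c) records randomization group and HbA1c date and value, so counting women above the threshold needs no new data. Route of entry to care is not listed on that form and may need one added item. If the investigators choose to act in both arms, a few Early-arm results must be handled in real time, and the SAP 4.1 analyses must account for the second route into care.
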